8.17. Infant Assessments

Infant Anthropometrics

PBRC IRB# 13020

Infant body weight will be obtained using a standard electrical infant scale with the infant undressed. Recumbent infant length will be measured using an infantometer with a stationary head-board, a moveable footboard and a built-in centimeter scale. Maximal head circumference will be measured by a standard measuring tape around the child's head, and abdominal circumference will be measured by a standard measuring tape around the child's abdomen. Length, weight, head circumference, and abdominal circumference will be performed by a trained research team member before 10 days of life.

PEAPOD

Body composition will be assessed in infants with air displacement plethysmography (Life Measurement Inc, Concord, CA), as previously described [28, 29]. The infant will be placed in a special chamber called a PEA POD (pictured). The infant will lay naked in the supine position on a flat tray that slides into a transparent plastic chamber. The amount of volume (space) occupied by the infant will be measured. The staff will be able to monitor the child during the test through the transparent top.

Infant Skinfold Thickness

Infant skinfold thickness will be measured at four sites (tricep, subscapular, iliac crest and thigh) by a trained research team member before 10 days of life using Harpenden skinfold calipers.

9. PARTICIPANT SAFETY AND CONFIDENTIALITY

This study does not involve major risk to participants. Efforts to minimize the potential risks of the assessment methods and outcome variables include frequent monitoring by the investigators to assure that no volunteer suffers any adverse effects from participating in the research. Risks of complications will be reduced by carefully selecting participants for treatment. Other than subjects being obese at the time of enrollment, the inclusion and exclusion criteria were created to ensure women with low risk for pregnancy complications are included. The subjects' primary care obstetrician will be informed of the study procedures and purpose and will be required to provide medical clearance for the subject to participate in the proposed study. Medical clearance will also be obtained by the Medical Investigator. The Medical Investigator will communicate all adverse and serious adverse events to the primary care obstetrician and the development of any pregnancy-induced contraindications will be disclosed by the primary care physician to the Medical Investigator. Patients and the primary care obstetrician will be made aware of any abnormal findings determined throughout the course of the proposed study.

9.1. Risks to participants

- Accelerometry. There is no risk associated with measuring activity with accelerometers. The accelerometers used for outcome measurements in the proposed research (SenseWear and ActiGraph) fit comfortably on the participant's arm and wrist. In rare cases, the device(s) may irritate the skin; if this occurs, the device(s) can easily be removed should they become uncomfortable.

- Archive of Biological Samples: The primary risk to participants who donate biospecimens to be banked for future research is the risk of loss of confidentiality and/or privacy. Participants will be given a chance to approve/disapprove on the consent form the taking of extra blood for further research purposes. Storage and disposal of tissue will be conducted in a manner conforming to the appropriate care and handling of biological specimens as outlined through the Institutional Biohazard Committee Guidelines.
- Blood draw: There is the possibility of pain and bruising at the vein on the arm where the needle is inserted. Aseptic (sterile) technique and trained personnel minimize these risks.
- Body weight: There is no known risk to participants who measure/record their body weight.
- BOD POD: Air displacement plethysmography by BOD POD® (Life Measurement Inc, Concord, CA) will be used to measure body composition in the participants. Measurement of whole body adiposity with the BOD POD® is non-invasive and completely safe for use during pregnancy [74].
- Collection of urine: There is no known risk to participants in collecting their urine.
- Doubly labeled water: The safety and ethical considerations for the use of stable isotopes in humans and specifically in studies of special populations including pregnant women and infants is reviewed in an International publication from the International Atomic Energy Agency [75]. Stable isotopes have been used in studies of human metabolism for more than 50 years and no significant adverse event has been documented [76]. Stable isotopes of several elements such as hydrogen, oxygen and carbon have widespread use in clinical research. Deuterium and oxygen-18 or ¹⁸O are stable isotopes for hydrogen and oxygen, respectively. The two atoms occur naturally in the body and the dose given in the water is not dangerous. The dosage of deuterium is typically 20-80 mg per kg of body weight which results in a maximum concentration in body water of ~0.16% [76, 77]. Deuterium has been given to humans including pregnant women up to a stable concentration of 0.5% for several days [78]. The threshold of deuterium toxicity is 15.0% and this concentration far exceeds doses administered to humans [79, 80]. The doubly labeled water we will use in this study in pregnant women will raise the deuterium concentration in body water to about 1/50th of the threshold for toxicity. There is no evidence regarding untoward effects of deuterium for the measurement of total energy expenditure in humans including pregnant women [75]. The biological effects of oxygen-18 are small. For example, replacement of up to 60% of body oxygen with oxygen-18 did not result in any adverse effects [80]. Given the low risk associated with the use of stable isotopes in humans, deuterium and oxygen-18 are considered safe for use in humans across the lifespan. The use of doubly labeled water for measuring energy expenditure has been used in various special populations such as pregnant and lactating women, infants (including premature infants) and children [24-28]. Measuring energy expenditure in pregnant women with doubly labeled water at the planned doses carries no known risk.
- Indirect calorimetry in a metabolic chamber: Measuring energy expenditure in the metabolic chamber carries no known risk. Some participants may experience claustrophobia or discomfort from staying in the chamber however they will have close contact with metabolic core and inpatient staff during the chamber stay.
- Infant assessments. There are no known risks to infants from participation in this study. Some newborns will begin to cry during the gentle handling necessary to undress the infant and to perform measurements such as length and weight. This is a normal occurrence. If infants cry while being measured, he or she will be comforted by holding, covering with a warm blanket, gentle rocking, or a diaper change, if necessary.
- Maternal food intake: Food intake will be estimated with the Remote Food Photography Method (RFPM). The RFPM involves taking pictures of food selection and plate waste and is not associated with significant risk. Considerable effort has been expended to make these procedures as user-friendly and unobtrusive as possible.
- MRI: The risks associated with MRI include the discomfort of being in a small space, noise from the scanner, and extraction of metal lodged in the body. Subjects with any implanted metal device will be excluded. Subjects will be offered lumbar and/or leg support if uncomfortable. We have significant experience performing whole-body MRI scans on adults and have not experienced any issues thus far. While there are no known risks of MRI on the pregnant woman or fetus, the National Radiological Protection Board advises that these tests be done after the first trimester. Therefore, the first MRI will be scheduled at or after 13

weeks, and only after there has been an ultrasound confirming gestational age. The study equipment contains magnets that are at or below the strength of the magnets used in safety studies. A standard MR pre-study questionnaire will be filled out to screen for: presence of a pacemaker, presence of metallic objects, either surgically placed or otherwise, history of claustrophobia. An investigator or MR technician will ensure that no metallic objects are in the subject's possession before they enter the MR suite.

- Oral glucose tolerance test: The glucose drink may cause nausea, vomiting, abdominal bloating, or a headache. The blood draw may be associated with pain or bruising where the needle is inserted. Trained personnel and aseptic (sterile) techniques are used to minimize these risks.
- Self-report Questionnaires: There are no anticipated risks from completing self-report questionnaires. If signs of minor stress or fatigue are apparent, participants will be given time to take a break from completing the questionnaires. It is estimated that the questionnaires will take from 35 to 50 minutes to complete. The questions contained in some of the questionnaires may make people feel uncomfortable since they ask about topics such as how they feel about their body size. Responses to the questions will be coded to protect confidentiality, and participants may choose to not answer questions.
- Ultrasound: There are no known risks associated with obstetric ultrasound.

9.2. Safety Monitoring/Adverse Events

The following findings would generate a safety alert and study staff should be notified immediately:

1. High Score on the Beck Depression Inventory II
 - Actively suicidal
 - BDI-II question 9 value of 2 or 3 (regardless of BDI-II total score) requires notification of the Principal Investigator (PI) or a designated clinician with appropriate training in mental health assessment. The research staff should wait with the patient until the PI or designated clinician (Pennington psychiatric staff with coordination by the social work department) has the opportunity to assess the participant. The PI or designated clinician should assess the patient for risk of imminent harm to self and contact emergency services if needed. If the PI or designated clinician is not immediately available, notify emergency services according to local standards. Research staff should wait with the participant until emergency services has assumed care.
 - Severe depression
 - BDI-II score of 29-63 (and BDI-II question 9 value of 0 or 1) requires that research staff inform the participant about her elevated score and notify the PI or designated clinician who should assess the patient for safety and/or possible psychiatric referral. If the PI or designated clinician is not immediately available, the participant may leave unattended, but the PI/ designated clinician should contact the participant within 24 hours to assess her for risk of imminent harm and should contact emergency services if needed. The participant should be told to expect such contact from study personnel. The patient's prenatal care provider also should be informed within 2 business days.
 - Moderate depression
 - BDI-II score of 20-28 (and BDI-II question 9 values of 0 or 1) requires that the participant be informed and that it is recommended she see her physician or mental health professional for further evaluation. Participants may be provided with materials on available mental health resources.
2. High Blood pressure
 - If measured blood pressure is $\geq 160/110$, i.e. systolic blood pressure ≥ 160 mm Hg and/or diastolic blood pressure ≥ 110 mm Hg, study staff will call the participant's prenatal care provider immediately and have a Pennington Biomedical physician or nurse practitioner meet with participant and confirm measures. The physician or NP will initiate the action plan.
 - If measured blood pressure is $\geq 140/90$, i.e. systolic blood pressure ≥ 140 mm Hg and/or diastolic blood pressure ≥ 90 mm Hg, study staff will instruct participants to contact their provider regarding the

PBRC IRB# 13020

elevated measure to arrange appropriate follow-up. Additionally, study staff will notify the prenatal care provider by phone before the end of the study visit.

- At least one blood pressure reading must meet criteria when two readings are taken, and at least two blood pressure readings must meet criteria when three readings are taken.
3. Weight loss from enrollment weight during pregnancy
- Alert values will be weight loss of 6% or greater of enrollment weight for women who were obese at enrollment.
 - For the first weight loss alert, the research staff will notify the patient, discuss her energy balance activities.
 - The patient will be asked to notify prenatal care provider and will be given weight measurement to report to prenatal care provider.
4. Fetal Growth
- Ultrasound alert abnormalities will be determined by physician [name]
5. Infant Growth
- If the infant weight measured is indicative of a $\geq 12\%$ weight loss from birth weight (reported by the parent/legal guardian at the visit), the research staff will notify the infant participants' parent/legal guardian and a referral will be made to the infant's pediatrician with the assistance of the study's medical investigator.
 - If the infant growth safety alert is triggered, the medical investigator or IPU nurse practitioner will be called prior to the conclusion of the study visit for further evaluation of the infant.

An **adverse event** is any untoward medical occurrence including but not limited to:

- Musculoskeletal injury that requires medical attention
- Fetal growth restriction (<5th percentile with abnormal umbilical artery Dopplers)
- Unanticipated untoward medical events

Pennington Biomedical Research Center is an AAHRPP accredited institution and, above all else, is committed to ensuring and maintaining the safety of its participants. Study co-investigator, [name] [name], directs the Maternal Fetal Medicine Department at Woman's Hospital in Baton Rouge, Louisiana. [name]. [name] will review all MRI scans within 14 days and will follow standard institutional reporting procedures for reporting any abnormal findings. We will use the provided definitions of Adverse Events and Serious Adverse Events. Events will be reported according to our institutional reporting policy.

Although MRI scans and ultrasound images are collected during the study for research purposes only, it is possible that research physician or radiology staff may notice something that could be important to the health of the participant. Should such findings arise from these procedures, the research physician or research staff will contact the participant and/or the participant's primary healthcare provider with information about the findings. The participant and/or their healthcare provider may also receive a copy of the images pertaining to these findings.

A **serious adverse event** (SAE) is defined as an unanticipated medical occurrence that is deemed associated with study participation by the study Medical Investigator that results in one of the following:

- Death
 - Maternal death
 - Fetal or infant death, including miscarriage, therapeutic abortion because of increasing signs of maternal or fetal compromise, and stillbirth.
- Life-threatening event
 - Life threatening events in the mother or fetus are defined as those that in the view of the research staff and PI put the individual patient at imminent substantial risk of dying, or if continued participation in the study might have resulted in death.
- Hospitalization (initial or prolonged)

- Maternal hospitalization or acute outpatient evaluation (e.g. in an emergency room or labor and delivery triage unit) alone is not sufficient to qualify as a serious adverse event. Hospitalization or acute outpatient evaluation for the following would not be considered a serious adverse event: term delivery, preterm premature rupture of membranes (pPROM), pyelonephritis, bedrest, contractions, ruling in or out preeclampsia, and preterm labor.
- Any infant hospitalization after neonatal discharge and during the infant's participation in the study is reported as a serious adverse event.
- Any medical or surgical procedure performed (e.g., surgery, transfusion) itself is not the adverse event; instead, the condition that leads to the procedure is the adverse event.
- Disability or permanent damage
 - If the adverse event resulted in a substantial disruption of the mother or infant's ability to conduct normal life functions, i.e., the adverse event resulted in a significant, persistent or permanent change, impairment, damage or disruption in the patient's body function/structure, physical activities and/or quality of life. The recommendation for bedrest does not constitute an SAE.
- Medical Intervention to prevent permanent impairment or damage

Other serious important medical events also qualify. When an event does not fit the other outcomes, but may jeopardize the patient and may require medical or surgical intervention or treatment to prevent one of the other outcomes, this should also be reported as an SAE.

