8.1.5. Surveillance and Reporting Procedures

All AEs (except for expected) will be reported. Adverse events will be documented during the scheduled visits. For each sign, symptom or adverse event, the following information will be recorded:

- A brief descriptor of the adverse event
- Start and stop dates
- Intensity (mild / moderate / severe)
- Whether the AE was "serious" or not (as defined below)
- Causal association with the intervention assigned (none / doubtful / possibly / probably / very likely)
- Outcome (resolved / resolved with sequelae / improving / still present and unchanged / death)
- Action taken with respect to the intervention (none / intervention temporarily discontinued / medical therapy required / intervention permanently discontinued / other).

Serious adverse events that are deemed unanticipated and related and therefore required to be reported to the IRB will be telephoned, faxed, or emailed *within 48 hours* of ascertainment by the center PI or study coordinator to the local Institutional Review Board. Because a written record of notification is required, telephone notifications must be followed with written documentation that the IRB has been informed. Unanticipated and related SAEs not resolved by the end of the study or that have not resolved upon discontinuation of the subject's participation in the study will be followed by the clinical site until the event resolves, stabilizes or returns to baseline.

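### The SAE definition in section 9.2 requires an event to be unanticipated and study-related, so serious outcomes judged unrelated or anticipated are left out of the SAE count, and this conflicts with the section's own infant-hospitalization rule

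*Combined protocol and SAP*

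**What the plan says.** Section 9.2 (Safety Monitoring/Adverse Events) gives two definitions. An adverse event "is any untoward medical occurrence including but not limited to" a short list of examples, and no causality condition is attached. A serious adverse event is "an unanticipated medical occurrence that is deemed associated with study participation by the study Medical Investigator" and that results in one of several outcomes.

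The death outcome sits under that lead-in. It covers maternal death and "Fetal or infant death, including miscarriage, therapeutic abortion because of increasing signs of maternal or fetal compromise, and stillbirth". Under hospitalization, the section first lists maternal admissions that do not count as SAEs, such as term delivery, pyelonephritis and preterm labor. It then says: "Any infant hospitalization after neonatal discharge and during the infant's participation in the study is reported as a serious adverse event".

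The reporting section, numbered 8.1.5 although it follows 9.2, lists the items recorded for each event. Two of them are "Whether the AE was 'serious' or not (as defined below)" and "Causal association with the intervention assigned (none / doubtful / possibly / probably / very likely)". Outcome is a further item, with death as one of its values. The 48-hour notice applies to "Serious adverse events that are deemed unanticipated and related and therefore required to be reported to the IRB", and follow-up to resolution applies to "Unanticipated and related SAEs not resolved by the end of the study" or by the time the participant leaves the study. The section opens by saying that adverse events are reported unless they are expected.

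**The concern.** Seriousness, relatedness and expectedness are three different judgements. Section 9.2 folds the second and third into the first. One person's causality decision then determines whether a death or stillbirth enters the SAE count, before anyone can compare events across participants.

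The participants are obese pregnant women, their fetuses and their newborns, and section 9 describes the study as not involving major risk. If that description is right, most serious outcomes will probably be judged unrelated to the study, and those are the events the definition takes out of the count.

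Staff also face a practical problem. An infant admission judged unrelated is excluded by the lead-in and included by the hospitalization rule.

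**Working it through.** No arithmetic applies. The check is to set the rules side by side and see where each kind of event falls.

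**Notation.** Let S be the events with an outcome listed in 9.2, after the maternal hospitalization exclusions. Let U be the unanticipated events and R the events the Medical Investigator deems study-related.

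**Step 1: the definition.** Under the lead-in, SAE = S ∩ U ∩ R. The events in S that are not SAEs are those outside U, outside R, or outside both.

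**Step 2: classify cases.**

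| Event | SAE by the 9.2 lead-in? | Other rule that applies |
|---|---|---|
| Stillbirth, unanticipated, judged related | Yes | 48-hour IRB notice |
| Stillbirth or maternal death, unanticipated, judged unrelated | No (fails R) | Adverse event; causality can be none and outcome can be death |
| Life-threatening event, anticipated | No (fails U) | Adverse event, but may be exempt from reporting as expected |
| Infant hospitalization after neonatal discharge, judged unrelated | No (fails R) | 9.2 also says it is reported as an SAE |

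The last row is a contradiction inside 9.2. The second and third rows show which events leave the SAE count.

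**Step 3: the qualifier in 8.1.5.** Restricting SAEs to those that are unanticipated and related gives (S ∩ U ∩ R) ∩ U ∩ R = S ∩ U ∩ R, which is the same set. The qualifier appears twice, for IRB notice and for follow-up, and selects nothing either time. If the infant rule is treated as an exception to the lead-in, the qualifier acts on those admissions only.

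**Step 4: the exemption for expected events.** An anticipated event in S fails the SAE definition. If expected in 8.1.5 means the same as anticipated, the event also falls outside adverse event reporting. Neither word is defined. The text also does not say whether the exemption covers recording as well as reporting.

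**Step 5: effect of removing the two conditions.** With SAE = S, the 48-hour filter selects S ∩ U ∩ R, the same set as under the lead-in now. Expedited reporting is unchanged, and only the SAE log grows.

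**Sign of poor alignment.** Section 8.1.5 says serious is defined below, but the only definition comes before it. Its causality item refers to an assigned intervention in a single-arm study, whereas 9.2 refers to study participation.

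**The case against.** The strongest reply has four parts.

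- **No rival definition in 8.1.5.** A reader might infer that the reporting section contradicts the definition. The documents do not support that. 8.1.5 does not define an SAE, a redundant qualifier can still be followed, and a causality item is needed for non-serious events in any case. This part stands: the conflict lies inside 9.2, and 8.1.5 shows redundancy.
- **The events are not lost.** A reader might also infer that unrelated deaths go unrecorded, or that a pattern across events could not be seen. That is not supported either. Such events meet the adverse event definition and are logged with causality and with death as an available outcome, so they can be found. What they lose is the serious label. This stands for unrelated events, but is less secure for anticipated ones because of the exemption.
- **The infant rule can be read as a specific exception.** The word any may only contrast with the maternal exclusions just before it, or may override the general lead-in. Both readings are workable, but they lead to different counts and the text does not choose between them.
- **Little depends on the count.** The analysis plan (10.2) does not use SAE counts, and the stopping section (9.3) names injury rates, recruitment and dropout. Section 9.2 also defers to an institutional reporting policy that is not in the documents. This limits the weight of the point. It does not remove it, because 9.2 says that its own stated definitions will be used.

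**Conclusion.** The point holds in a limited form. As written, the SAE definition excludes maternal deaths, stillbirths and life-threatening events judged unrelated or anticipated. It conflicts with the infant-hospitalization rule in the same section and leaves the qualifier in 8.1.5 redundant. The consequence is an SAE count filtered by causality and expectedness. Unrelated events remain on the adverse event log; anticipated ones may also go unreported there.

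The number of events affected cannot be derived from the documents. The conclusion assumes that the lead-in governs the sub-items beneath it, as the layout indicates. The further gap for anticipated events assumes that expected and anticipated mean the same thing. Whether the institutional policy separately captures unrelated deaths cannot be determined here.

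This is worth correcting because the safety count should not depend on a prior causality decision and the remedy is cheap. It does not affect the primary analysis.

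**What to change.** Reconcile sections 9.2 and 8.1.5 as follows.

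1. In 9.2, remove the two conditions (unanticipated, and deemed associated with study participation) from the SAE definition, so that seriousness follows the listed outcomes. Keep the listed maternal hospitalization exclusions as they stand. The infant rule then agrees with the lead-in.
2. In 8.1.5, record relatedness and expectedness as separate judgements for every event. A causality item already exists; its wording should refer to study participation. An expectedness item should be added. Correct the pointer to the definition of serious.
3. Use unanticipated and related only as the filter for 48-hour IRB reporting and for follow-up of unresolved events.
4. State that the exemption for expected adverse events does not apply to events with a serious outcome.

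The cost is a wording amendment and a few more entries on the SAE log. Expedited IRB reporting and the primary analysis do not change.
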